9.2.2.1 Inclusion/Exclusion Criteria

Patients in the study will be required to meet the following inclusion criteria:

- The patient has at least one prescription of linaclotide in his/her medical records anytime during the study period in the UK; for Spain and Sweden, inclusion will be determined by at least one dispensation of linaclotide).
- Patient has at least 12 months of computerised records prior to the first use of linaclotide (index date).
- Patient is active (i.e., alive and permanently registered) at index date.

The following exclusion criteria will apply:

- Patient has no follow-up time (for example, transfers out or dies on the date of the first linaclotide prescription).

Additionally, in the UK two additional exclusion criteria will be applied:

- Patient who does not meet the CPRD 'acceptable' criteria (patient is permanently registered at the practice and has a valid year of birth and gender) at index date (or equivalent for other database)
- The practice's up-to-standard (UTS) date in CPRD is later than the index date (practices meeting pre-defined quality control standards for completeness, continuity, and plausibility are registered as UTS since the date those standards are met), or equivalent for other database

No additional exclusion criteria will be applied in Spain or Sweden since all records are considered of sufficient quality to conduct research studies.

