9.2.2.2 Time Periods and Dates

The study period is determined by the launch date of linaclotide and subsequent uptake. The study period starts on the date of linaclotide commercialisation in each of the countries: in UK in May 2013, in Spain in September 2014, and in Sweden in February 2013.

The end of the study period is defined by the last day of patient records in the available data cut, currently planned for 31 December 2017, to allow for sufficient follow-up time (long-term use) to have

the opportunity to accrue a sizable number of subjects for descriptive purposes, and for subpopulations of interest (those with potential off-label use and potential for abuse/excessive use). Please refer to the Study Size and Data Analysis sections below.

[figure not shown]
Additionally, the database's lag time (for collected data to be available in each database, estimated as up to 8 months) needs to be factored in to determine when data will be available.

Index date (or cohort entry date) will be defined as date of the first prescription (UK) or dispensation of linaclotide (Spain and Sweden). Baseline period will be the ≥ 12 -month period before index date.

The follow-up period for each study subject will be the time from the index date to the earliest of the following dates (end of follow-up date; one day is the minimum follow-up; Figure 1):

- End of the study period for follow-up
- Disenrollment from the database (date of transfer out of the practice)
- Date of last data collection
- Death
- 1.5 times the number of days of linaclotide supply after the expiry of the last linaclotide prescription during the study period (for a total of 2.5 times the last prescription duration) plus one additional day when a potential discontinuation could be assessed (please refer to section 9.3.3 Linaclotide Treatment Outcomes below)

Figure 1. Study Periods Linaclotide DUS

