 - Bacterial/viral/parasite lab information, when available (positive versus negative or no information)

For prevalence of chronic comorbidities, prior diagnoses, or history of digestive surgery at index date, the patient's entire medical history will be explored.

9.3.3. *Linaclotide Treatment Outcomes*

Secondary outcomes of this study will be linaclotide treatment patterns. The linaclotide exposure information is characterised by the linaclotide days of supply. Days of supply will be ascertained from the prescription/dispensation information recorded in the databases and the recommended dose (one capsule of linaclotide 290 µg taken once per day) and calculated by dividing the quantity prescribed/dispensed by the daily dose. Days of supply of one prescription/dispensation are expected to be around 28 days since the 28-capsule pack will be the most widely used package size. If package size is unknown, then the median duration for patients with this information will be used (and if no median can be estimated then 28 days will be used).

Linaclotide prescription patterns of interest are:

- Discontinuation of linaclotide: defined as no prescription of linaclotide in the period of 1.5 times the number of days of supply of the last linaclotide prescription following its expiry date (Sikka et al., 2005; Peterson et al., 2007): for example, for a 28-day prescription, no new prescription in the 43 days after the expiry date of the prescription supply. The date of discontinuation is the day after the date of expiry of the last linaclotide prescription. Time to discontinuation (permanently during the study period or temporarily) is the interval between the date of the first linaclotide prescription and the date of discontinuation. Discontinuation

will be reported separately for those who permanently discontinue during the study period and for those who discontinue temporarily and subsequently restart on linaclotide (see below).

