- Switching from linaclotide to laxatives, antispasmodics, prokinetics, or antidepressants without prescription of linaclotide: defined as a prescription of laxatives, antispasmodics, prokinetics, or antidepressants that starts while on treatment with linaclotide and continues after the date of the linaclotide discontinuation. The date of switching is the date when the new prescription of laxatives, antispasmodics, prokinetics, or antidepressants is issued followed by linaclotide discontinuation. Time to switching is the interval between the date of the first linaclotide prescription and the date of switching.

To be able to define linaclotide discontinuation and switching at the end of the study period, it is necessary to have enough study period for follow-up after the expiry of the last linaclotide prescription. This time at the end of the study corresponds to the gap tolerated between prescriptions that could occur if the patient is on treatment but also hospitalized or travelling. This grace period is defined as 2.5 times the number of days of supply of the last linaclotide prescription (the prescription duration in addition to 1.5 times the number of days of supply of the last linaclotide prescription following its expiry date) plus one additional day when a potential discontinuation (or switching) could be assessed. Patients who continue taking linaclotide will be censored at the end date of the study period for linaclotide utilisation. This has implications for the interpretation of linaclotide treatment duration because it is conditioned by the study length.

Switching from linaclotide requires discontinuation in the prescription of linaclotide but these patterns will be considered exclusive events and patients experiencing switching immediately after discontinuation will be allocated to switching. Time to discontinuation and time to switching to another drug are secondary endpoints for the linaclotide utilisation study.

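### Discontinuation takes 43 days to confirm but is dated back to supply expiry, and no run-out covers transfer, death or last data collection, so stopping is slightly underestimated

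*Protocol*

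**What the plan says.** All of this is in the protocol.

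- **Event (9.3.3).** Discontinuation needs a gap of 1.5 times the last supply. The example for a 28-day prescription is "no new prescription in the 43 days after the expiry date of the prescription supply".
- **Date of the event (9.3.3).** "The date of discontinuation is the day after the date of expiry of the last linaclotide prescription".
- **End of the study (9.3.3).** To define the outcome there, "it is necessary to have enough study period for follow-up after the expiry of the last linaclotide prescription". "This grace period is defined as 2.5 times the number of days of supply of the last linaclotide prescription", plus one day. Then: "Patients who continue taking linaclotide will be censored at the end date of the study period for linaclotide utilisation". Section 4.9 also describes patterns up to the end of this utilisation period.
- **Follow-up (9.2.2.2).** It runs to the earliest of several dates: the end of the study period for follow-up, "Disenrollment from the database (date of transfer out of the practice"), last data collection, death, or 2.5 times the last supply plus one day after the last prescription. The minimum is one day. The only calendar end given is 31 December 2017.
- **Analysis (9.7.2).** Patterns are assessed over the follow-up period already defined, which is the one in 9.2.2.2.
- **Entry (9.2.2.1).** "The patient has at least one prescription of linaclotide in his/her medical records anytime during the study period in the UK"; for Spain and Sweden, at least one dispensation. Entry is not closed before study end.

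**The concern.** An event that is dated early but confirmed late can be recorded only if the patient stays under observation through the gap. Take two patients who both let a first 28-day pack lapse. One is observed for a year and has an event on day 29. The other transfers out on day 60, has no event, and contributes time at risk up to day 60, as if still treated between days 29 and 60. The first is counted as stopping and the second as persisting, although they behaved alike.

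The error has one direction: discontinuation comes out too low. It is largest around the first pack, where Section 9.5 expects about one third of patients to stop. It affects the Kaplan-Meier curves and the numbers and proportions promised in 9.7.2.

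**Working it through.** **1. The windows.** Section 9.3.3 states: "Days of supply of one prescription/dispensation are expected to be around 28 days".

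- Gap after expiry: 1.5 × 28 + 1 = 43 days, which reproduces the plan's example.
- Grace period: 2.5 × 28 + 1 = 71 days = 28 + 43.
- With the index date as day 1, a one-pack user's supply ends on day 28, the event is dated day 29, and it is confirmed on day 71, 42 days after its date.

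**2. Who is caught at the calendar end if there is no run-out.** 31 December 2017 minus 71 days is 21 October 2017. A one-pack stopper who starts after that cannot be confirmed. Shares of the cohort, assuming even entry within 2017 (Table 3 stops at 2016):

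- UK, repeating the 2016 increment: 2,674 − 1,211 = 1,463; 1,463 × 71/365 = 285; 285/(2,674 + 1,463) = 6.9%.
- UK, assuming 2,400 entrants in 2017: 2,400 × 71/365 = 467; 467/(2,674 + 2,400) = 9.2%.
- Sweden, repeating the 2016 increment: 4,584 − 2,766 = 1,818; 1,818 × 71/365 = 354; 354/(4,584 + 1,818) = 5.5%.

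**3. Who is caught on any reading.** Patients who transfer, die or reach last data collection inside an open gap. The grace period in 9.3.3 is tied to the end of the study and does not reach them. The last follow-up rule in 9.2.2.2 (2.5 times supply plus one day) does not help either, because the earliest date applies.

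**4. Size.** Kaplan-Meier estimates from 60,000 simulated patients per scenario.

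- From the protocol: 28-day packs, and entry weights for the first three years of 1,872, 5,085 − 1,872 = 3,213 and 9,665 − 5,085 = 4,580 (Table 3, combined).
- Assumed: 4,580 repeated for the fourth year, refill gaps of 0 to 14 days, yearly loss of 0 to 20%, and three stopping patterns built on Section 9.5. The run-out is 71 days.

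One-year cumulative discontinuation (%):

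| Pattern | Yearly loss | True | No run-out | Run-out at study end only | Run-out at every end |
|---|---|---|---|---|---|
| 40% yearly rate | 10% | 32.7 | 31.1 | 32.4 | 32.8 |
| 40% yearly rate | 20% | 32.5 | 30.5 | 31.7 | 32.4 |
| One third stop at first pack, few later | 0% | 38.6 | 37.2 | 38.7 | 38.7 |
| One third stop at first pack, few later | 10% | 38.7 | 36.7 | 38.2 | 38.6 |
| One third stop at first pack, few later | 20% | 38.8 | 36.3 | 37.8 | 38.8 |
| Heavier stopping throughout | 0% | 73.5 | 71.7 | 73.5 | 73.5 |
| Heavier stopping throughout | 10% | 73.6 | 71.2 | 73.1 | 73.6 |
| Heavier stopping throughout | 20% | 73.0 | 70.1 | 71.9 | 72.9 |

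Across all scenarios:

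- **No run-out:** 1.3 to 2.9 points low, with 4.5 to 8% of true discontinuations unrecorded.
- **Run-out at study end only:** at most about 0.1 point low with no loss, 0.2 to 0.3 at 5%, 0.3 to 0.5 at 10%, and 0.8 to 1.2 at 20%.
- **Run-out at every end:** within about 0.1 point of the truth.

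**5. A second simulation, no run-out.** Inputs: one third stopping after one pack, the rest with a mean of about 400 days, UK-like intake with 2,400 entrants in 2017, and 8% yearly loss (the last three assumed). Results: 31.1% against a true 33.3% at day 30, 50.1% against 53.0% at day 180, and 68.0% against 71.2% at one year. Sweden-like intake with 3% loss is 1.2 to 1.7 points low. Ending time at risk 42 days before each patient's end of follow-up recovers the truth within about 0.1 point.

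**6. A tempting repair that fails.** Censoring unresolved patients at supply expiry gives 31.2% against 32.7% (40% pattern, 10% loss). It censors true stoppers exactly at their event time.

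**The case against.** A reader might infer that the plan censors every patient with an open gap at 31 December 2017 and so understates discontinuation by 2 to 3 points. The documents do not support that:

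- The censoring sentence in 9.3.3 concerns patients who continue treatment, not those whose gap is unresolved.
- Section 9.3.3 foresees the problem at study end and sets a grace period for it. The utilisation period is named separately from the follow-up period, which reads naturally as utilisation closing first with the run-out between them.
- Figure 1, which is titled as showing the study periods, is not available here and may say so. Its absence is not a fault of the plan.

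This stands, and it limits the larger figures to the reading without a run-out. It is also true that the endpoints are secondary, that the study is descriptive with no a priori hypothesis, that 9.3.3 discloses that treatment duration depends on study length, and that the loss rates and the 2017 intake are assumptions. No distortion of the comparison of IBS-C with other indications has been shown.

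One could add that censoring dates are commonly left to the statistical analysis plan. That answers only part of the point. The protocol itself fixes the follow-up rules, and it names one period end in 9.3.3 and 4.9 and another in 9.7.2. The grace period depends on each patient's last supply, so no single calendar date follows from it. Annex 1 lists an analysis plan dated 7 June 2016, before the extension of 26 January 2017, so any calendar end it states needs rechecking.

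**Conclusion.** The point holds in a limited form. Late confirmation combined with back-dating biases Kaplan-Meier discontinuation downward for anyone whose follow-up ends inside the gap, and on no reading is there a run-out for transfer out, death or last data collection.

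If utilisation closes one grace period before study end, the bias is about 0.1 to 0.5 point at 3 to 8% yearly loss and about 1 point at 20%. If it does not, the bias is about 1 to 3 points. Which case applies cannot be settled from the readable text. All these sizes rest on assumed loss, intake and stopping patterns; the direction does not. It is a small, cheaply removed bias in a secondary endpoint, and it leaves the baseline and off-label descriptions untouched.

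**What to change.** In 9.3.3 and 9.7.2:

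1. Reconcile the two period ends and state the utilisation end date.
2. For the treatment-pattern analyses, end each patient's time at risk one fixed confirmation gap (43 days for 28-day packs) before the earliest of study end, transfer out, last data collection and death. Do not subtract it from an end of follow-up that is itself set by a completed gap.
3. Count only discontinuations or switches dated on or before that date, and leave out patients with no time before it.
4. Keep all patients in the baseline and off-label descriptions.

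Two details should be settled when writing this. Longer supplies need a longer gap (1.5 × supply + 1). A switch is dated while the linaclotide supply is still running, so its confirmation can take up to the full grace period (71 days for a 28-day pack); that length is the safer one for the switching analysis.

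Cost: a sentence or two, one derived date per patient, and about 43 days of person-time per patient (71 where the longer gap is used). No further data are needed.

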9.3.4. IBS Diagnosis and Severity Definition

The target indication of linaclotide is the treatment of moderate to severe IBS-C in adults. There are several Read, ICD-9 or ICD-10 codes related to IBS, but none are specific to IBS-C. In order to identify potential cases of IBS-C patients using codes, a combination of an IBS code with a code for constipation will be used. Table 4, Table 5 and Table 6 in Annex 3 include a broad list of Read codes, ICD-10 and ICD-9 codes for the identification of patients with IBS with different level of specificity, and codes for constipation to be used in combination.

There are no Read, ICD-9, or ICD-10 codes to indicate the severity of IBS. The most studied and most commonly used tools for measuring IBS severity involve quality-of-life and patient-reported symptom metrics that are not routinely recorded in the computerised databases selected for this study. Some components like symptoms or number of healthcare visits (part of the Functional Bowel Disorder Severity Index [Drossman et al., 2011]) have been previously used in the development of an IBS severity measure. However, it is not envisaged that this will be done as part of this study.

9.4. Data Sources

In the UK, the proposed data source is the CPRD; for Spain, the proposed data source is the SIDIAP; and for Sweden the NPR linked to the PDR. A summary of potential data sources that were evaluated for use in the study can be found in the *Database Feasibility Assessment* section in Annex 3.

9.5. Study Size

The study sample size calculations are based on real and projected post-authorisation usage data information provided by Almirall [MAH of linaclotide at the time of development of this protocol]. The estimated patient use by year after the introduction of linaclotide for the three countries of interest is shown in Table 2.

Table 2. Projected Post-authorisation Use of Linaclotide per Year in Countries of Interest (Number of Patients derived from Sales and Projected Sales of Linaclotide Capsules)

Country	2014	2015	2016	2017
Sweden	1,238	2,475	3,263	4,052
Spain	1,889	9,385	16,435	23,073
UK	7,475	14,419	27,619	45,279

Source: Data provided by Almirall [MAH of linaclotide at the time of development of this protocol] on January 2015
Abbreviations: UK=United Kingdom

The end of data collection was initially planned for December 2016 to allow for a minimum of one year of follow-up (long-term use) for approximately 25% of patients enrolled in the study and for subpopulations of interest to have the opportunity to accrue a sizable number of subjects.

To estimate the cumulative number of patients and patient-time use of linaclotide we assumed that:

- Linaclotide prescriptions are evenly distributed across each of the countries
- Each database captures data of a representative sample of the population
- The database patient base is constant over the forecast period and 90% of patients meet inclusion and exclusion criteria
- There is an approximately 40% yearly treatment discontinuation rate and an average treatment duration of 135 days per patient and year (approximately one-third of patients expected to cease medication after one pack of linaclotide or 28 capsules because of unsatisfactory response; one-third of patients expected to use the medication for an average of 150 days out of 365 because of clinically meaningful benefit; approximately one-third expected to use medication almost continuously for an average duration of treatment calculated at 220 days per year)

Based on the above assumptions, the number of patients initially anticipated in each of the countries available for analyses was as described in Table 3.

Table 3. Projected Post-authorisation Cumulative Number of IBS-C Patients using Linaclotide in the CPRD from the UK, PDR from Sweden and SIDIAP from Spain, and Corresponding Number of Patient-years, 2014–2016, Meeting Inclusion and Exclusion Criteria for Linaclotide DUS*

	2014	2015	2016
CPRD: 8% of the UK			
projected number of patients	518	1211	2,674
projected number of patients-years	211	557	1,219
SIDIAP: 12.8% of Spain			
projected number of patients	207	1,108	2,407
projected number of patients-years	76	456	1,122
Sweden National Patient Register: 95% of Sweden			
projected number of patients	1,147	2,766	4,584
projected number of patients-years	506	1,250	2,231
Combined:			
projected number of patients	1,872	5,085	9,665
projected number of patient-years	794	2,263	4,572

*86% in Sweden and Spain, 81% in the UK, of the total number of linaclotide users
Abbreviations: CPRD=clinical practice research datalink; UK=United Kingdom

By the end of 2016 it was estimated that over 9,650 patients would have been exposed to linaclotide

in the three target databases together, for a combined exposure of more than 4,500 patient years. The UK would be contributing approximately 28% of patients, Spain 25%, and Sweden 47%.

For the treatment patterns, a total of approximately 8,800 patients would allow the detection of a hazard ratio of 1.2 or greater for patient characteristics, assuming linaclotide discontinuation or linaclotide switching occur in about 10% the observed sample (users with a specific characteristic) with a probability of 40%, with 90% power and a two-sided type I error rate (alpha) of 5%.

In the progress report for 2016, users of linaclotide included in each of the study databases were reported to be below the targeted numbers. Following the recommendation of the PRAC rapporteur, the end of the data collection was then extended by one year until December 2017 to allow for the number of users to reach the desired sample size.

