4.9. Data Analyses

All analyses will be first performed separately in each of the study countries. In addition, for the primary study objectives, aggregated analyses with data from all three countries will be performed.

Baseline analyses will be conducted to characterise linaclotide users, and socio-demographic and clinical variables will be described for all users and for those subgroups of patients who were not sufficiently documented in the clinical development programme. The number and percentage of patients using linaclotide off-label will be also described.

Further, linaclotide treatment patterns will be described from index date to end of study period for linaclotide utilisation. Kaplan-Meier estimates will be used to describe time to discontinuation in the prescription or dispensation of linaclotide; and to describe switching from linaclotide to another drug used in IBS-C (laxatives, antispasmodics, prokinetics, or antidepressants). To better assess differences in time to event by the alleged reason for linaclotide prescription (IBS-C or other condition), Cox regression analysis will be employed if the proportional hazards assumption holds; if not, more complex models will be proposed, including predictor variable interactions with time.

Statistical analyses will be conducted using SAS® statistical software.

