9.7. Data Analysis

Analyses will be performed in each of the study countries separately.

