To better assess differences in time to event by the alleged reason for linacotide prescription (IBS-C or other conditions), Cox regression analysis will be employed. Multivariate Cox regression models will be fitted to identify the effects of the indication and various other baseline variables on the time from initiation of linacotide to first treatment discontinuation or switching. For each of the two outcome variables (time to discontinuation and time to switching), a set of plausible candidate models will be proposed and fitted to the data. Models will be ranked according to Akaike's Information Criterion and the best model will be selected; or, if several models prove to perform well, these will be averaged to produce a final model. Some iteration between choosing candidate models and data analysis will likely be necessary, owing to the need to check that the proportional hazards assumption holds for each candidate model.

Statistical analyses will be conducted using SAS® statistical software.

9.8. **Quality Control**

Standard operating procedures at each research centre will be used to guide the conduct of the study. These procedures include internal quality audits, rules for secure and confidential data storage, methods to maintain and archive project documents, quality-control procedures for programming, standards for writing analysis plans, and requirements for senior scientific review.

All work will be subject to quality control and documentation procedures to make certain the final report is accurate and thorough and the analyses can be reproduced. If the data do not permit an analysis as planned (e.g., through insufficient sample size in a subgroup analysis) or if clarifying analyses are required (e.g., an unexpected result that could be explained by a subgroup analysis), [REDACTED] staff will inform Allergan and include the additional information and results in the report. All key study documents, such as the analysis plan, abstraction forms, and study reports, will undergo quality-control review, senior scientific review, and editorial review.

A quality-assurance audit of this study may be conducted.

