SIDIAP is a primary care database launched in 2010, following the steps of CPRD or THIN in the UK, that collects longitudinal data from EMR from 274 primary care centres in Catalonia since 2006. Catalonia is a region with a total of 5.8 million patients who represent approximately 12% of the Spanish population (4% of the Spanish population in SIDIAP-Q with higher quality indicators). Data is updated once a year and there are several scientific publications using this data source and reporting validation study results. The date of the latest available data is December 2013, and 2014 data will be made available by May–June 2015.

Data from primary and specialised care, hospital and pharmacy data are available, as well as patient characteristics such as gender and date of birth, GP-diagnosed conditions, GP prescriptions, prescription dosing and size, date of prescription and dispensation, laboratory test results, other procedures, specialist referrals and diagnosis, hospital referrals, hospital procedures, and discharge diagnosis death rate, and pregnancy information. GP diagnoses are coded following the ICD-10 codes, and hospital admissions following the ICD-9.

SIDIAP does not transfer data to private entities, but it can carry out quality investigation projects (Bolívar et al., 2012) and submit on their completion the corresponding reports on results, which will be agreed upon with the funding body in the design stage of the study. It also allows the possibility to contact physicians (currently a group that includes 10% of the total) for extracting additional information on the patient through a questionnaire.

SIDIAP is considered to be an appropriate source of data for the execution of this as the vast majority of its patients have two and three or more years of follow-up and the database itself can link with the Drug Dispensation databases (and additionally with the Mortality Registry for Death Cause); both characteristics are relevant for the proposed linaclotide study. The objectives were reviewed by their research team who are confident about the utilisation study. They identified some challenges for the safety study, and recommended performing a preliminary descriptive and exploratory study to confirm feasibility of conducting the study and to improve the validity of the actual study results.

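### The 90% power stated for the treatment-pattern models needs about 8,800 patients combined, but the protocol plans those models country by country, where the same inputs give 40% to 65%

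*Protocol*

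**What the plan says.** **Power statement.** Section 9.5 claims for the treatment patterns that "a total of approximately 8,800 patients would allow the detection of a hazard ratio of 1.2 or greater for patient characteristics". The assumptions are that the events "occur in about 10% the observed sample (users with a specific characteristic) with a probability of 40" per cent, "with 90% power and a two-sided type I error rate (alpha) of 5" per cent.

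**Unit of analysis.** Section 9.7 opens with "Analyses will be performed in each of the study countries separately", and a comment in the Annex 2 checklist (section 8) says the same. The abstract (4.9) makes one exception: "for the primary study objectives, aggregated analyses with data from all three countries will be performed".

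**Status of the outcomes.** Section 8.1 names patient characteristics and off-label use as the primary questions and prescription patterns as the secondary one. Section 9.3.3 confirms it: "Time to discontinuation and time to switching to another drug are secondary endpoints for the linaclotide utilisation study".

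**Models.** Section 9.7.2 plans multivariable Cox models. "For each of the two outcome variables (time to discontinuation and time to switching"), it proposes a set of candidate models. It mentions no pooled or country-stratified version.

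**Projected patients.** For the end of 2016, Table 3 gives 2,674 in the UK, 2,407 in Spain and 4,584 in Sweden, 9,665 combined. Section 9.5 adds that the 2016 progress report found users below target in each database, and that data collection was extended to December 2017.

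**The concern.** A power statement is useful only if it belongs to an analysis that will be run. The 8,800 is a total across databases, whereas the Cox models it is meant to support are planned within one country at a time. The single exception, in the abstract, covers objectives that do not include these models.

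At stake is how country-level results will be read. Section 8.2 lists describing the effect of indication on time to discontinuation or switching, and section 9.7.2 adds other baseline variables. If a country model shows no clear association for an uncommon characteristic, a reader who relies on section 9.5 may take that as good evidence against a hazard ratio of 1.2. The model would not have had the power for that conclusion.

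**Working it through.** **Inputs, all from the protocol.** Hazard ratio 1.2, two-sided 5%, power 90%, prevalence of the characteristic p = 0.10 and event probability 0.40 (section 9.5); country counts (Table 3).

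**Step 1. Reproduce 8,800.** Schoenfeld's formula for a binary covariate:

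events = (z₀.₉₇₅ + z₀.₉₀)² / [p(1 − p)(ln HR)²] = (1.960 + 1.282)² / [0.10 × 0.90 × (ln 1.2)²] ≈ 3,512

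patients = 3,512 / 0.40 ≈ 8,780

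This matches the stated figure. At exactly 8,800 patients the power is 90.1%. The wording of the 10% and 40% is awkward, but the reversed reading (40% prevalence, 10% events) needs 13,180 patients and does not match. So 8,800 is correct under the stated inputs.

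**Step 2. Which data set reaches it?** Only the combined projection (9,665) does. The largest single country, Sweden, has 4,584.

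**Step 3. Power in the planned unit of analysis.** For N patients, with ln 1.2 = 0.1823:

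power = Φ(√(N × 0.40 × 0.09) × 0.1823 − 1.960)

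HR detectable with 90% power = exp[(1.960 + 1.282) / √(N × 0.40 × 0.09)]

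| | N (Table 3, 2016) | Events at 40% | Power for HR 1.2 | HR detectable, 90% power |
|---|---|---|---|---|
| UK | 2,674 | 1,070 | 43% | 1.39 |
| Spain | 2,407 | 963 | 40% | 1.42 |
| Sweden | 4,584 | 1,834 | 65% | 1.29 |
| Combined | 9,665 | 3,866 | 92.5% | 1.19 |

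**Step 4. The extension to 2017.** Table 3 stops at 2016. As a deliberately generous bound, assume that every 2017 user in Table 2 is new, and multiply by database coverage and by 90% eligible:

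- UK: 2,674 + 45,279 × 0.08 × 0.9 ≈ 5,934; power 76%
- Spain: 2,407 + 23,073 × 0.128 × 0.9 ≈ 5,065; power 69%
- Sweden: 4,584 + 4,052 × 0.95 × 0.9 ≈ 8,048; power 87%

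Even this bound, which ignores the reported shortfall, brings no country to 90%.

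**Step 5. Sensitivity to the scenario (assumed values, Table 3 counts, HR 1.2).**

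| Prevalence | Event probability | UK | Spain | Sweden |
|---|---|---|---|---|
| 10% | 40% (protocol) | 43% | 40% | 65% |
| 30% | 40% | 78% | 74% | 95% |
| 50% | 40% | 85% | 81% | 97% |
| 10% | 80% | 72% | 67% | 91% |

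Sweden passes 90% in these more favourable scenarios; the UK and Spain do not.

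**Step 6. What pooling would deliver.** The information in the three country estimates adds up: 1,069.6 × 0.09 + 962.8 × 0.09 + 1,833.6 × 0.09 = 347.9. This equals 3,866 × 0.09. If the hazard ratio is common and prevalence is similar across countries, inverse-variance pooling of the country log hazard ratios has about the power of the combined row. Heterogeneity between countries would lower it.

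**The case against.** **The study is descriptive.** Section 7 states that there is no a priori hypothesis, the outcomes are secondary, and no decision rule depends on a hazard ratio of 1.2. This stands and limits the consequence. It does not make the sentence correct, since the protocol chose to state a power.

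**The SAP may pool.** Annex 1 lists a separate SAP, which is not at hand, and section 9.7 omits even the aggregation that the abstract promises, so it may not be exhaustive. That is possible. The protocol's own text still attaches a combined number to analyses it describes as separate, and that wording needs correcting in any case.

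**The scenario is narrow.** The 43%, 40% and 65% hold only for a characteristic present in 10% of users with 40% events. This stands. A reader might infer that the IBS-C versus other contrast is underpowered to the same degree. The protocol gives no prevalence for that contrast, and step 5 shows that power could be much higher.

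**The 40% may be low or high for a given outcome.** A reader might infer that, because discontinuation and switching are mutually exclusive, each must have fewer events than the calculation uses. Section 9.5 can also be read as 40% for either outcome, so this is not established. Section 9.5 also gives about 40% as a yearly discontinuation rate, so cumulative events over a longer follow-up could exceed it.

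**The extension.** A reader might infer that the extra year was justified by the 8,800. Section 9.5 speaks of targets in each database and a desired sample size, and the abstract (4.8) also cites long-term use and subgroups. Neither names 8,800.

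**Conclusion.** The point holds as a mismatch between sample size and analysis for a secondary objective. It is not an arithmetic error: 8,800 follows from the stated inputs. What fails is its application, because the protocol describes no combined treatment-pattern analysis.

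In the protocol's own scenario, country-level power falls short of the stated 90% by about 25 percentage points in Sweden, 47 in the UK and 50 in Spain. These figures rest on the Schoenfeld approximation, 10% prevalence, 40% events and full achievement of the 2016 projections. Counts that stay below target would lower them. The patient-characteristic and off-label results do not depend on this sentence.

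**What to change.** Choose one of two changes.

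**(a) Restate by country.** Replace the 8,800 sentence in section 9.5 with the detectable hazard ratio, or the power, for each country. Use the counts accrued to date, give the assumed prevalence of the characteristic, and say whether the 40% applies to each outcome or to both combined.

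**(b) Add a pooled estimate.** Add to section 9.7.2 an inverse-variance pooling of the three country log hazard ratios. State that the 8,800 / hazard ratio 1.2 / 90% claim applies only to that pooled estimate, and only if the 40% event probability holds for the outcome being modelled. Annex 3, part B notes that "SIDIAP does not transfer data to private entities"; pooling summary estimates needs no patient-level transfer. The abstract (4.9), section 9.7 and the Annex 2 comment should then say the same thing about aggregation.

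Option (a) costs a few lines and a less favourable stated power. Option (b) costs a paragraph and one extra results table. Neither needs new data.
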